### **ADDITIONAL STUDY INFORMATION**

#### **Description of SmartPill**

The SmartPill GI Monitoring System includes an ingestible capsule, a receiver, a receiver docking station and display software. The capsule houses sensors for pH, temperature, and pressure, and has the ability to transmit the sensed data at 434 MHz to a receiver worn by the subject. The portable receiver worn by the subject receives and stores data; the MotiliGI software provides calculations and graphical displays to the physician. After activation and ingestion, the capsule signals are transmitted from within the GI tract and are captured by a receiving antenna incorporated into the receiver, which also provides an interface for data transmission to a PC as well as connections for battery charging. The capsule functions for at least 5 days after activation and has a pH range of 0.5 to 9 with an accuracy of  $\pm 0.5$  pH units. The pressure sensor has a pressure range of 0 to 350 mm Hg with an accuracy of 5 mmHg. The temperature sensor has a range of 25° to 49°C, with an accuracy of  $\pm 0.8^\circ\text{C}$ .

### **SmartPill Study Procedure**

Patients taking gastric acid suppressants will be instructed to stop proton pump inhibitors 1 week prior to the colonic transit study and histamine type 2 receptor antagonists 3 days prior to the colonic transit study. Patients with constipation will stop treatments for constipation at least 72 hours prior to the study and for the 5 days of the study. This includes enemas, cathartics, PEG solutions (including Miralax, enulose). Patients with constipation may take medications to help stimulate a bowel movement with either milk of magnesia, 2.4 to 4.8 grams (30-60 ml), or magnesium citrate, 11 to 25 grams daily in 1 or more doses, up to 48 hours prior to SmartPill ingestion.

All study subjects will report for the ingestion visit after an overnight fast (beginning at midnight). Date of the start of the last menstrual period for female subjects will be recorded.

The SmartPill capsule will be activated and calibrated. All study subjects will ingest a SmartBar (a nutritional bar) consisting of approximately 254 calories with 120 cc of water, followed by the SmartPill Capsule with 50 ml of water. The subject may drink an additional 50 ml of water if difficulty swallowing capsule for a total of 100 ml with capsule ingestion. Ingestion of the meal, SmartPill Capsule, and water should be completed within 10 minutes.

Intraluminal GI tract pH, pressure, temperature will be measured continuously with the SmartPill capsule. Once the capsule is ingested the patient is free to leave to the facility. At 8 hours after capsule ingestion, with the subject in a sitting position, one can of regular Ensure (Vanilla, lactose-free, 8 fluid ounces [237 ml]; 250 calories) will be ingested.

All study subjects will maintain a diary and will record times of bowel movements, meals, gastrointestinal symptoms (pain/discomfort, nausea, vomiting), and supine/sleeping times. Subjects will be instructed, if they wish, to recover and return the SmartPill capsule along with the diary and receiver at the end of the study. If they are unable to return to the office due to distance, they will be given material to send the items via FedEx.

### **Endoscopic Mucosal Resection Procedure**

EMR uses a standard cap device which fits over the end of the endoscope. EMR is used frequently in current practice at the MGH for upper and lower GI tract lesions.

## **BIOSTATISTICAL ANALYSIS**

Descriptive statistics based on a series of 50 patients for histologic and dysmotility findings. Univariate and multivariate regression analysis of relationship between motility parameters, histologic disease state and GI symptoms in Fabry patients.

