### **SPECIFIC AIMS**

#### **Primary Aim – Dysmotility**

The primary goal of the study is to gain further comprehension of the pathophysiology underlying dysfunction of the gastrointestinal tract and to correlate the abnormal findings with symptoms in an attempt to further classify the disease manifestation. This investigation will be achieved by examining the gastric, small bowel and colon emptying time. Additionally, neurologic and myopathic changes will be analyzed through evaluation of contractility, pH and temperature of the bowel as measured by the SmartPill study. These results will be correlated with the patient's subjective gastrointestinal symptoms in an attempt to elucidate a causational relationship between functional abnormalities with presentation.

The aim in this phase of the study is to gain additional understanding of the disease manifestation via motility abnormalities in order to improve symptom targeted therapy. The hypothesis is that patients with Fabry disease will have abnormal motility which will correlate with the patients symptoms and quality of life as noted on the questionnaires.

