### *Exclusions Criteria:*

1. Fabry disease with other concomitant gastrointestinal diagnosis (Example: Inflammatory Bowel Disease, Celiac Disease)
2. Pregnancy
3. Endoscopic mucosal resection exclusions:
  - a. Any contraindication to conscious sedation,
  - b. Contraindication to endoscopy,
  - c. Untreated or unmanageable coagulopathy,
  - d. Thrombocytopenia (<50).
  - e. Patient on ERT for more than 6 months.
4. Exclusions for SmartPill:
  - a. Previous history of bezoars.
  - b. Prior GI surgery except for cholecystectomy, appendectomy, or Nissen fundoplication.
  - c. Any abdominal surgery within the past 3 months
  - d. History of diverticulitis, diverticular stricture, and other intestinal strictures
  - e. Tobacco use within eight hours prior to capsule ingestion and during the initial 8-hour recording on Day 0 or the Ingestion visit.
  - f. Alcohol use within eight hours prior to capsule ingestion and throughout the entire monitoring period (5 days).
  - g. BMI > 38
  - h. Allergies to components of the SmartBar
  - i. Use of medical devices such as pacemakers, infusion pumps, or insulin pumps.
  - j. Uncontrolled diabetes with a hemoglobin A1C greater than 10.

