### Prohibited Medications for SmartPill

1. No medications which may alter gastric pH around the time of the study, which includes:
  - a. Proton Pump Inhibitors for 1 week (examples: omeprazole, lansoprazole and esomeprazole, pantoprazole, rabeprazole)
  - b. Histamine2 Blockers for 3 days [(examples: cimetidine (Tagamet HB), famotidine (Pepcid), and ranitidine hydrochloride (Zantac), nizatidine (Axid)]

- c. Antacids for 1 day (examples: Maalox, Mylanta, Amphogel, Tums, Rolaids)
2. No medications that affect gastrointestinal motility for 3 full days before the start of the study and during the 5 ensuing days of study including but not limited to those drugs listed below:
  - a. Prokinetic agents, such as metoclopramide (Reglan), tegaserod (Zelnorm), domperidone (Motilium), erythromycin, zithromycin, cisapride
  - b. Anti-emetics agents, such as phenergan, compazine
  - c. Narcotic analgesic agents, such as methadone, fentanyl, percocet
  - d. Anticholinergic agents for IBS – Bentyl, Levsin
  - e. Medications for constipation, including enemas, cathartics, polyethylene glycol solutions (including Miralax), and lactulose (e.g., enulose). Patients with constipation may take medications to help stimulate a bowel movement with either milk of magnesia, 2.4 to 4.8 grams (30-60 ml), or magnesium citrate, 11 to 25 grams daily in 1 or more doses, up to 48 hours prior to SmartPill ingestion.
  - f. 5HT3 antagonists, such as Lotronex (alosetron hydrochloride) and Zofran (ondansetron hydrochloride).
  - g. Anti-diarrheal agents, such as Kaopectate (attapulgit, donnagel, rheaban), Pepto-Bismol (bismuth subsalicylate), Imodium (loperamide), and lomotil (atropine diphenoxylate).
  - h. Opiate agents used to treat diarrhea.

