### **SmartPill Capsule Ingestion Visit (Visit 2)**

This study visit should take about 2 hours to complete.

At this visit, the test procedure will be explained to the subject. They will then ingest the SmartBar, a standardized meal used to accurately measure gastric emptying time, within 10 minutes. Following ingestion, the subject will swallow the SmartPill capsule with 70cc of water. They will then receive the SmartPill receiver to carry for the duration of the study, lasting 5-7 days.

During the initial 8 hours after capsule ingestion the subject you will not be allowed to sleep because sleep may affect motility.

The subject will remain NPO for 8 hours after ingestion of the capsule. They will drink a bottle of Ensure 8 hours after ingestion. An hour after drinking the Ensure, the subject can return to their normal eating habits. Instructions will be given to the patient about completion of the daily diary in which they will document periods of ingestion, sleeping patterns and bowel movements in addition to marking it on the receiver. They will also be instructed to wait 5 minutes after each bowel movement to ensure recording of possible passage of the SmartPill.

Prior to leaving, the subject will schedule a follow up visit (visit #3) to return the receiver and the diary and discuss any questions about the study. If the patient has travelled a far distance to participate, they will be given instructions on mailing the receiver and diary back to the office.

After the visit, the subject will keep the receiver at no more than 5 feet from their body at all times during the 5-7 day period. They will be instructed to refrain from any strenuous activities during the study period. The prohibited medications will be reviewed. Additionally, they will again be asked to refrain from alcohol use for the duration of the study.

If the subject is unable to make two visits, they will be given the option to condense the first and second visit into one visit. The visit would last about 2 hours long. Prior to scheduling the condensed visit, the subject will receive an electronic copy of the consent form, in accordance with Partners Information Security guidelines, and will be notified of all medications that need to be stopped for the SmartPill. Any questions will be answered and all information about the SmartPill test will be provided.

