### **Follow Up Visit (Visit 3)**

This study visit should take about 30-45 minutes to complete and will take place 5 to 7 days after Visit 2.

At this visit, the patient will return the SmartPill receiver and the study diary. We will discuss any questions or concerns they had about the study. If available, we will review the results of the SmartPill test. If it is unclear that the capsule has passed, based on the subject's history or on the study results, we may prescribe erythromycin as a promotility medication or obtain a KUB for verification.

If the patient cannot return the receiver in person, they will be provided with information on mailing the receiver back. Once the results have been reviewed, the patient will be contacted to provide the results of the SmartPill and confirmation of capsule exit.

If the patient is appropriate for the endoscopic mucosal resection, this will be scheduled within the following 3 weeks.

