### **Power**

Based on prior studies examining gastric emptying time (GET), there was found to be a 70% correlation between abnormal gastric emptying time and symptomatic patients. Additionally, in order to have significant power for regression analysis, 25 patients with positive symptom association with gastric emptying time would be needed. Therefore, based on the 70% correlation of symptoms to GET, 35 patients need to have abnormal GET. Based on the results from Argoff et al, 5 out of 7 (70%) of Fabry patients with symptoms of gastroparesis including nausea and early satiety, had delayed gastric emptying time. Thus, extrapolating to this study, 50 Fabry patients will need to be examined for dysmotility, in order to obtain the 35 patients with delayed gastric emptying time for analysis and correlation.

Additionally, larger cohort size enables use of multivariate correlation with increased usage of symptom and demographic variables. However, study size remains restricted due to likely limited patient availability.

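### Does the missing rule for transit times left unfinished when SmartPill recording ends call for a change to the analysis plan?

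*Combined protocol and SAP*

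**What the plan says.** The primary aim rests on "examining the gastric, small bowel and colon emptying time", together with contractility, pH and temperature, all to be related to symptoms. The Biostatistical Analysis section has two sentences: descriptive statistics on 50 patients, and "Univariate and multivariate regression analysis of relationship between motility parameters, histologic disease state and GI symptoms in Fabry patients". It does not say whether transit time is the outcome or the predictor, and it has no rule for incomplete times.

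Observation is limited. Under Visit 2 the patient is given a "receiver to carry for the duration of the study, lasting 5-7 days", and the device description says "The capsule functions for at least 5 days after activation". The risk section accepts that a capsule may stay in the stomach or may not be expelled within the week. The responses are clinical or serve to verify exit: at Visit 3, if exit is unclear, "we may prescribe erythromycin as a promotility medication or obtain a KUB for verification", and the risk section adds evaluation by a gastroenterologist.

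The Power section uses gastric emptying as a category: "35 patients need to have abnormal GET".

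**The concern.** A segment that the capsule entered but did not leave before the signal stopped has a time known only to exceed the observed one. Ordinary regression software omits a blank value. The omission would not be random, because a time is unfinished mainly when it is long. Dropping such patients would understate how often that segment is delayed, weaken the motility-symptom correlation, and bias the slope if transit is the outcome. The colon is most exposed, since it gets only what is left of the 5 to 7 days after the stomach and small bowel. Some Fabry patients are constipated, and treatments for constipation are stopped for the test. In a rare-disease series of 50, losing informative patients would be a pity, and choosing the handling after seeing the data would be poor practice.

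**Working it through.** **The plan's own figure.** 25/0.70 = 35.7 (the plan has 35; with the exact 5/7, 25/(5/7) = 35.0), then 35/0.70 = 50. The chain reproduces. It counts patients with abnormal gastric emptying. A capsule still in the stomach when recording ends can be classed as delayed without knowing the exact time, so the count of 35 does not depend on the missing rule. Even if one delayed patient were dropped outright, 35/50 = 70.0% would become 34/49 = 69.4%.

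**How many patients.** The protocol gives no rate of non-exit by day 5 to 7 in Fabry disease. Its risk section gives two proxies: one capsule held in the stomach among 326 adults (caught in a bulk-forming agent), and 0.75% retention of another capsule in patients without known stenosis. The higher rate for known stenosis is not the relevant one, because the exclusions list "History of diverticulitis, diverticular stricture, and other intestinal strictures". With n = 50, the expected number is 50p and the chance of at least one is 1 − (1 − p)^50.

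- p = 1/326: 50p = 0.15; chance of at least one 14.2%, of none 85.8%.
- p = 0.0075: 50p = 0.38; chance of at least one 31.4%, of none 68.6%.
- Exact 95% upper limit for 1/326: 1.70%, so 50p = 0.85.

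**What dropping them does.** The plan states no alpha or effect size. Assumed here: bivariate normal data, correlation 0.40, n = 50, two-sided 0.05, 40,000 simulated trials. The slowest k patients are removed (complete-case analysis), or kept as ties at the slowest rank.

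| k | Pearson power, slowest dropped | Pearson power, k dropped at random | Slope, transit as outcome | Slope, transit as predictor | Rank power, ties kept |
|---|---|---|---|---|---|
| 0 | 0.833 | 0.833 | 0.400 | 0.398 | 0.786 |
| 1 | 0.790 | 0.827 | 0.369 | 0.398 | 0.786 |
| 2 | 0.754 | 0.819 | 0.347 | 0.398 | 0.786 |

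**Does a rule help?** Compare always dropping with a rule that uses Pearson when nobody is unfinished and tied ranks otherwise. Weight by the binomial probabilities of k = 0, 1 and 2 or more, treating more than 2 as 2.

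- p = 1/326 (0.8576, 0.1319, 0.0105). Dropping: 0.8576×0.833 + 0.1319×0.790 + 0.0105×0.754 = 0.8265. Rank rule: 0.8576×0.833 + 0.1424×0.786 = 0.8263.
- p = 0.0075 (0.6863, 0.2593, 0.0544). Dropping: 0.6863×0.833 + 0.2593×0.790 + 0.0544×0.754 = 0.8176. Rank rule: 0.6863×0.833 + 0.3137×0.786 = 0.8183.

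Against 0.833 with no loss, dropping costs 0.65 and 1.54 points. The rank rule recovers practically none of it. Ranks beat dropping only when two or more are unfinished, which has probability 1.0% and 5.4%.

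**A slower colon.** Three assumed scenarios, with no source in the documents: colon time log-normal with median/log-SD 24 h/0.62, 30 h/0.62 and 30 h/0.70; upstream time with median 9 h; window 120 to 168 h. They give on average 0.16, 0.44 and 0.87 unfinished patients of 50. Complete-case Pearson power is 0.828, 0.814 and 0.795; ranks used throughout give 0.791, 0.791 and 0.790. With transit as the outcome, the complete-case slope is 0.393, 0.383 and 0.369, and a Tobit model returns 0.402, 0.401 and 0.400. The Tobit test is slightly liberal at this size: power 0.847, 0.858 and 0.837 against 0.833, 0.846 and 0.827 with all times fully observed.

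**The case for a change.** The strongest reply is that both rates are poor proxies. Neither measures non-exit by day 5 to 7 in symptomatic Fabry patients, and the medication rules tend to slow constipated patients further: "No medications that affect gastrointestinal motility for 3 full days before the start of the study and during the 5 ensuing days of study". At an assumed 5% or 10% unfinished, complete-case power at correlation 0.40 falls to 0.735 or 0.663, and the slope with transit as outcome falls to 0.335 or 0.300, while tied ranks hold at 0.78 to 0.79. The monitoring section also has outcomes analysed as the study runs, so an unwritten rule could be chosen with results in view. A written sentence would cost almost nothing.

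The uncertainty about the rate stands, and so does the omission. Three things limit their weight.

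- Nothing in the documents supports 5% or 10%, and the plan does not say that unfinished patients are dropped or that transit is the outcome. The harm needs both a high rate and an assumed software default, and the slope bias also needs transit as the outcome.
- A simple rule can be worse than judgement. Failing to see the capsule leave is not the same as non-passage: the receiver may be out of range or the exit missed. The diary, history and any KUB help tell these apart. With windows of 5 to 7 days, tying at the slowest rank can also place a patient censored early above one observed to take longer. In the three colon scenarios this happens in 7% to 26% of trials that have a non-passer.
- Rank correlation does not give the adjusted slopes of a multivariate regression, and a switch triggered by the data could leave segments analysed by different methods.

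**Conclusion.** No change to the plan follows. This is a gap in detail that analysts can fill sensibly: check exit against signal, diary, history and any KUB, report how many segments were unfinished, count verified non-passage as delayed, and allow for censoring if transit is modelled as the outcome. All of this uses data already collected.

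At the protocol's proxy rates, fewer than one patient in 50 is expected to be affected. The power loss from dropping such patients is about 0.65 to 1.54 points, the slope is biased only when transit is the outcome, and the sample-size count is unaffected. The rank remedy gains nothing measurable. A censored regression gains something only in one of the two model directions that the plan leaves open.

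This rests on the proxies being of the right order and on an assumed correlation of 0.40 with two-sided alpha 0.05. It would need another look if non-passage proved to be several percent or more.

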### **Power**

Based on prior studies examining gastric emptying time (GET), there was found to be a 70% correlation between abnormal gastric emptying time and symptomatic patients. Additionally, in order to have significant power for regression analysis, 25 patients with positive symptom association with gastric emptying time would be needed. Therefore, based on the 70% correlation of symptoms to GET, 35 patients need to have abnormal GET. Based on the results from Argoff et al, 5 out of 7 (70%) of Fabry patients with symptoms of gastroparesis including nausea and early satiety, had delayed gastric emptying time. Thus, extrapolating to this study, 50 Fabry patients will need to be examined for dysmotility, in order to obtain the 35 patients with delayed gastric emptying time for analysis and correlation.

Additionally, larger cohort size enables use of multivariate correlation with increased usage of symptom and demographic variables. However, study size remains restricted due to likely limited patient availability.

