## **BACKGROUND AND SIGNIFICANCE**

Fabry disease is an x-linked lysosomal storage disease defined by a deficiency of alpha-galactosidase, leading to the accumulation of a cell membrane derived glycolipid, globotriaosylceramide, and its metabolites within the cytoplasm and lysosomes of many types of cells, including endothelial cells, cardiomyocytes, renal glomerular cells, and neurons (Clarke, 2007). Gastrointestinal manifestations such as abdominal pain, diarrhea and nausea are prominent and, although typically non life-threatening, can frequently cause significant morbidity and burden in a patient's life. Recent studies have found that up to 50% (range of 16-70%) of patients with Fabry disease, including both males and females, experience gastrointestinal symptoms (Hoffman et al., 2007). The symptoms are typically one of the first presenting signs of Fabry disease, after acroparesthesia, with the mean onset in males at age 5 years and females several years later at 9.5 years. Although females present later, the severity of the symptoms equalizes as the patient ages (Hoffmann, Schwarz, Mehta, & Keshav, 2007).

The gastrointestinal symptoms can vary in intensity and can occur anywhere along the GI tract including the stomach, small and large bowel. They tend to progress in incidence over time. The most common complaint is abdominal pain with up to one third of adults endorsing this ailment and many children reporting it as their initial GI symptom (Hoffmann et al., 2007; Mehta et al., 2004). It is typically described as a cramping mid-abdominal pain worsened with meals and increased stress. Alterations in bowel habits is the next most common GI presentation, with many patients complaining of urgent, explosive, post-prandial diarrhea frequently necessitating significant lifestyle changes. Others, mostly female, experience constipation (Hoffman, 2007). Less common, but significant gastric symptoms are also reported including nausea, vomiting and early satiety. Patients describe decreased appetite, inability to tolerate many foods and feelings of bloating consistent with gastric dysmotility.

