Additionally, there has been only one published report of the underlying functional dysmotility analysis in these patients. In 1987, Argoff et al found that 5 out of 7 patients with gastric symptoms had delay in gastric emptying scan and responded well to metoclopramide, suggesting a similar neuropathy to that seen in diabetic gastropathy (Argoff et al., 1998). Although many of the presenting gastrointestinal symptoms seem to involve dysfunction of the whole gastrointestinal tract, additional motility testing examining the small and large bowel has not been completed in these patients.

As the underlying pathology remains unclear, there is no Fabry-specified protocol for evaluation of patients with gastrointestinal symptoms. Bloodwork is frequently completed for initial evaluation of symptoms including CBC and electrolytes, which are typically normal. Additional workup including imaging such as a KUB may be performed, which is also commonly without abnormalities. In some patients with persistence of concerning symptoms, it may be clinically necessary to complete further evaluation via colonoscopy to evaluate for underlying mucosal disease.

The treatment for the GI symptoms in Fabry disease was historically symptomatic, utilizing promotility drugs, neuromodulators and antibiotics. The management has progressed recently with the initiation of enzyme replacement therapy over the past decade with many patients starting the replacement at younger ages. Although enzyme replacement therapy has shown promising results with some decrease in symptom severity, GI complaints remain a significant cause of morbidity for some patients on ERT (Banikazemi et al., 2005; Barbey et al., 2007; Zarate & Hopkin, 2008). More in depth understanding of gastrointestinal symptoms pathophysiology in Fabry disease is acutely needed in order to develop more specific evaluation of the symptoms and advance the treatment of these patients. By gaining additional insight into

the characterization of symptoms and the relationship to dysmotility, we anticipate improved and more focused adjunct therapies for the patients.

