## **Inclusion/Exclusion Criteria**

### *Inclusion Criteria:*

1. Adults ages 18- 70 years who have diagnosed Fabry disease either by enzyme testing in males or by enzyme and/or genetically confirmed mutation in females.
2. Adults with Fabry disease having any gastrointestinal complaints within the past year.
3. Endoscopic Mucosal Resection ONLY – Symptomatic subjects necessitating a sigmoidoscopy who are enzyme replacement therapy naive OR less than 6 months of treatment.

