#### **Recruitment Procedures**

Patients will be recruited via the Massachusetts General Hospital lysosomal storage disease clinic. The study will be presented to all patients with Fabry disease who have had gastrointestinal symptoms within the past year. Additionally, we will contact physicians who care for Fabry patients via email and conferences to inform them of the study. If patients indicate they are interested in the study to their provider, the patient may be contacted if the provider refers the patient to the study staff. Flyers with the research coordinator's contact information will also be given to interested patients and providers at conferences. At conferences, if interested, patients will be given the opportunity to sign a form that would allow them to be contacted by the study staff to learn more about the study. Subjects identified through RPDR will

receive a recruitment letter signed by the PI and the patient's provider (Please refer to the Protocol Summary for additional information). We expect to enroll all patients over a two-year period.

1. SmartPill study and questionnaires regarding gastrointestinal symptoms, quality of life and psychiatric comorbidities (Please see “study procedures” for additional information) will be administered to approximately 50 patients.
2. Histology section – Recruit up to 15 treatment naive patients or patients with less than 6 months of therapy who have lower GI symptoms including abdominal pain and/or bowel movement alterations for which a sigmoidoscopy would be clinically warranted. An endoscopic evaluation with mucosal resection will be performed.

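### The case for 50 patients applies a delayed-emptying rate from patients with gastroparesis symptoms to a cohort enrolled for any GI complaint, leaves no margin, and does not support its claim of regression power

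*Combined protocol and SAP*

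**What the plan says.** The Power section builds the sample size in three steps.

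- For regression it states that "25 patients with positive symptom association with gastric emptying time would be needed".
- It divides this by a 70% figure linking symptoms to abnormal gastric emptying time (GET) and arrives at 35 patients with abnormal GET. The 70% is called a correlation but is used as a proportion. The studies behind it are not identified.
- It divides again by a delayed-emptying rate, citing that "5 out of 7 (70%) of Fabry patients with symptoms of gastroparesis including nausea and early satiety, had delayed gastric emptying time". The result is 50 patients, "in order to obtain the 35 patients with delayed gastric emptying time for analysis and correlation".

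Background and Significance describes the same source group: "5 out of 7 patients with gastric symptoms had delay in gastric emptying scan". The entry criterion is wider: "Adults with Fabry disease having any gastrointestinal complaints within the past year". After abdominal pain and changes in bowel habit, the background adds: "Less common, but significant gastric symptoms are also reported including nausea, vomiting and early satiety".

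Recruitment Procedures says that the SmartPill study and questionnaires "will be administered to approximately 50 patients". Biostatistical Analysis plans "Univariate and multivariate regression analysis of relationship between motility parameters, histologic disease state and GI symptoms in Fabry patients". Neither that section nor Power gives an effect size, alpha, power or number of predictors. Power does acknowledge that the number of available patients limits the study's size.

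**The concern.** The 5/7 rate was observed in patients selected for gastric symptoms, the group in which delayed gastric emptying is most to be expected. The plan applies it to every enrolled patient, including those who enter with only pain, diarrhea or constipation. No entry criterion or recruitment step enriches for gastric symptoms.

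The power claim is a separate fault. Regression power depends on the number of patients analysed, the size of the association, the test level and the model. The number of patients who turn out to have both delayed emptying and matching symptoms does not fix it.

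This paragraph is the only statistical argument for 50 patients, and it serves the primary dysmotility aim. If it fails, readers of the results would be relying on a yield and a power that the design never established.

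**Working it through.** **1. Reproduce the plan's figure.** Inputs from Power: 25 needed, 70% association, 5/7 taken as 70%.

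- 25 / 0.70 = 35.7, which the plan takes as 35.
- 35 / 0.70 = 50.0, as stated. With the unrounded rate, 35 / (5/7) = 49.
- Rounding up at each step gives 36, then 36 / 0.70 = 51.4, so 52.

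The chain reproduces. The starting 25 cannot be reproduced, because no inputs are given for it.

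**2. Margin if the plan's own rates hold.** Binomial with n = 50; a patient counts as associated with probability (association × delay rate).

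| Delay rate | Expected delayed | P(at least 35) | Expected associated | P(at least 25) |
|---|---|---|---|---|
| 0.70 | 50 × 0.70 = 35.0 | 0.57 | 35 × 0.70 = 24.5 | 0.50 |
| 5/7 | 50 × 5/7 = 35.7 | 0.65 | 35.7 × 0.70 = 25.0 | 0.56 |

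At 70%, the expected associated count falls short of the plan's own 25 because 35.7 was taken as 35.

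**3. What the any-complaint cohort would need.** Let g be the share of the cohort with gastric symptoms, with delay rate 5/7, and d the delay rate in the rest. An expected 35 of 50 requires g × 5/7 + (1 − g) × d = 0.70, so d = (0.70 − g × 5/7) / (1 − g). The documents do not give g, so a range is shown.

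| g (assumed) | d needed |
|---|---|
| 0.50 | (0.70 − 0.357) / 0.50 = 0.69 |
| 0.70 | (0.70 − 0.500) / 0.30 = 0.67 |
| 0.90 | (0.70 − 0.643) / 0.10 = 0.57 |
| 0.95 | (0.70 − 0.679) / 0.05 = 0.43 |
| 0.98 | (0.70 − 0.700) / 0.02 = 0 |

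So the cohort must consist almost wholly of patients with gastric symptoms, or delay must be nearly as common without them as with them.

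**4. Precision of 5/7.** The exact (Clopper-Pearson) 95% interval is 29% to 96%. Step 3 holds 5/7 fixed. With g = 0.50, the upper limit would lower the required d to (0.70 − 0.50 × 0.963) / 0.50 = 0.44. The lower limit would raise it to (0.70 − 0.50 × 0.290) / 0.50 = 1.11, which is impossible.

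**5. What the sample can detect.** Assumptions: one unadjusted correlation, two-sided alpha 0.05, 80% power, Fisher z. Detectable |r| = tanh[(1.960 + 0.842) / √(n − 3)].

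| Patients analysed | Detectable absolute r |
|---|---|
| 50 | 0.39 |
| 45 | 0.41 |
| 40 | 0.43 |
| 35 (delayed only) | 0.46 |

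If ten associations were tested with a Bonferroni correction (an assumption), each would use two-sided alpha 0.005. At n = 50: tanh[(2.807 + 0.842) / √47] = 0.49.

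**The case against.** The best defence is that this is an exploratory study in a rare disease. Power openly calls the step an extrapolation and admits that patient numbers are constrained. Descriptive statistics on 50 patients come first in the analysis section and need no particular yield. All of that stands, and it is a good reason to leave the sample size alone. It does not support the yield of 35 or the statement about regression power, both of which the plan chose to make. Had the plan simply omitted alpha, power and effect size, that would be missing detail. The fault is that it asserts power from a count that cannot supply it.

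Three stronger readings are tempting, and the documents do not support them.

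- *A shortfall in delayed patients would shrink the regression.* Power says that the 35 are for analysis and correlation, while Biostatistical Analysis describes the regression in Fabry patients generally. The text does not settle which set is meant. If all evaluable patients enter, a lower delay rate does not by itself reduce the sample.
- *Recordings will be lost.* Risks and Discomforts lists technical problems with the capsule as possible and gives no rate. The 45 and 40 in step 5 are therefore illustrations.
- *The interval for 5/7 gives the range for this cohort.* Multiplied by 50 it is about 15 to 48, but that would describe 50 patients like the seven in the source, not 50 enrolled for any GI complaint.

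**Conclusion.** The concern holds as a fault in the justification. The rate is taken from a more selected group than the one enrolled, and no adjustment is made. Even if 70% is accepted, the plan has only a 57% chance of its 35 and a 50% chance of its 25. The claim of regression power has no basis in the text.

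The probabilities in step 2 need only the plan's own rates and independent patients. The break-even rates rest on assumed shares with gastric symptoms and on 5/7 held fixed. The true delay rate in an any-complaint cohort is not in the documents, so the target of 35 is unsupported rather than shown to be unreachable.

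A reader might infer that 50 is miscalculated or must be raised. Neither follows: the division is correct apart from the rounding of 35.7, and a sample limited by availability is defensible if described as such.

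**What to change.** Keep the sample at about 50 and revise the text as follows.

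1. In Power, state that feasibility sets the sample size.
2. Delete the 35/25 yield, or replace it with an expected range for a cohort with any GI complaint. State the assumed share with gastric symptoms and the assumed delay rates.
3. Reconcile Power with Biostatistical Analysis on whether the regression uses all evaluable patients or only those with delayed GET. Using all evaluable patients gives more precision (detectable |r| 0.39 with 50, against 0.46 with 35), but the choice is the investigators'.
4. Replace the power claim with the detectable association for the chosen set, from step 5 of the working, with its assumptions: a single unadjusted association, 80% power, two-sided alpha 0.05.
5. Add that multivariable models, or testing many associations, would need larger effects. The ten-test figure of about 0.49 can serve as an example, labelled as an assumption.

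The cost is one reworded paragraph and one sentence on the analysis set, with no extra patients or procedures. The drawback is that the plan's stated expectation becomes less favourable.
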